5.3.4.2 Supplementary Analyses for Primary Endpoint(s)

To support the primary analyses, the following supplementary analyses will be conducted:

- For intercurrent events of study withdrawal, lost to follow-up, and death where censoring is planned for Day 29, censor at the time associated with the intercurrent event.

5.4 SECONDARY ENDPOINT(S) ANALYSIS(SES)

Estimands for all secondary endpoints are defined in [Table 2](#).

5.4.1 Key/Confirmatory Secondary Endpoint(s)

5.4.1.1 Proportion of Patients with ≥ 1 COVID-19-Related Medically Attended Visit

COVID-19-related medically attended visits are defined as hospitalization, emergency room (ER) visit, urgent care visit, physician's office visit, or telemedicine visit, with the primary reason for the visit being COVID-19. The statistical method is detailed in Section [5.1](#).

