The study consists of two periods: a 5-day treatment period and a 28-day safety and efficacy follow-up period, with mandatory study visits on Days 1, 2, 3, 5, 7, and 14. Some of these visits may be conducted by mobile nursing or telemedicine. In addition to mandatory study visits, there will be telephone calls on Day 21 (± 2 days) and Day 28 (± 2 days). The end of study visit will take place on Day 33 (± 3 days), preferentially as a telephone consult but may be conducted in-person in some instances, such as if the

patient is enrolling in a longer-term follow-up RO7496998 (AT-527) study. The total study duration for each patient will be approximately 33 days.

Based on local COVID-19 isolation policies, such as those in Japan, some study visits may be conducted in a hospital or similar facility. Patients in these countries will meet eligibility criteria as per protocol but may be hospitalized for the sole purpose of isolation and not for severe symptoms or inpatient treatment.

At study visits, patients will be assessed through physical examination, vital signs including peripheral capillary oxygen saturation (SpO₂), concomitant therapies, clinical laboratory tests, nasopharyngeal (NP) swabs, Nasosorption, and saliva samples (see [Appendix 1](#) for details regarding the timing of these assessments). In addition, PK samples will be collected from adult and adolescent patients at the timepoints indicated in [Appendix 2](#). A cohort of 65 adult patients may also undergo optional intensive sampling for pharmacokinetics and biomarkers. Patients will be closely monitored for COVID-19 signs and symptoms, COVID-19-related medically attended visits, and adverse events; adverse events will be graded according to National Cancer Institute Common Terminology Criteria for Adverse Events (NCI CTCAE) v5.0.

[figure not shown]
Throughout the treatment and safety-follow-up periods, patients will record symptoms in the COVID-19 Symptom Diary (see [Appendix 4](#)) and record body temperature (see [Appendix 3](#)). Temperatures will be recorded four times daily (morning, noon, evening, and bedtime) on Days 1–5, BID (morning and evening) on Days 6–10, and once daily in the evening on Days 11–29. COVID-19 symptoms will be recorded BID (morning and bedtime) on Days 1–14 and once daily (bedtime) on Days 15–29.

If patients are hospitalized during the study treatment period, follow-up visits should continue until study end if possible.

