4.1.2 Exclusion Criteria

Patients who meet any of the following criteria will be excluded from study entry:

- Clinical signs indicative of COVID-19 illness requiring hospitalization defined as any of the following:
 - In adults: respiratory rate \geq 30, heart rate \geq 125 bpm, SpO₂ \leq 93% on room air
 - In adolescents: respiratory rate \geq 30, heart rate \geq 130 bpm, SpO₂ \leq 93% on room air
- Admitted to a hospital prior to randomization or is hospitalized (inpatient) at randomization due to COVID-19

Note: If local policy requires COVID-19 isolation or internment in a hospital or similar facility, such as in Japan, but those patients otherwise meet the inclusion criteria, this exclusion may not apply.

- In the opinion of the investigator, is likely to experience imminent deterioration and require hospitalization
- Treatment with an investigational drug within 5 half-lives or 3 months (whichever is longer) of randomization
- Treatment with a COVID-19 therapeutic agent including, but not limited to, other direct or indirect acting antivirals *against SARS-CoV-2 (such as remdesivir or favipiravir), systemic or inhaled steroids (such as dexamethasone or inhaled budesonide), colchicine, ivermectin, interferons, convalescent plasma, monoclonal antibodies against SARS CoV-2 or interleukin 6 (IL-6), intravenous immunoglobulin or other EUA-approved treatments within 3 months or less than 5 drug elimination half-lives (whichever is longer) prior to the screening visit*
- Concomitant use of P-glycoprotein (P-gp) inhibitors or inducers listed in Section 4.4.3
- Known allergy or hypersensitivity to components of study drug
- Pregnant or breastfeeding, or intending to become pregnant during the study or within 30 days after the final dose of RO7496998 (AT-527)

Women of childbearing potential must have a negative pregnancy test result at screening prior to initiation of study drug.

- Abnormal laboratory test results at screening, defined as meeting any of the following sets of criteria:
 - ALT or AST $>5 \times$ upper limit of normal (ULN)
 - Total bilirubin $>1.5 \times$ ULN, unless the patient has known Gilbert disease
 - Creatinine clearance $<60 \text{ mL/min}$
 - Total WBC $<2,500/\text{mm}^3$ or ANC $<800/\text{mm}^3$
 - Platelet count $<80/\text{mm}^3$

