4.5.6.3 Additional COVID-19 Related Assessments

Self-Reported Temperature

Patients will measure temperature four times a day between Days 1 and 5, BID between Days 6 and 10, and once daily between Days 11 and 29 (see [Appendix 3](#)).

COVID-19 Related Medically-Attended Visit(s) Assessment

A COVID-19-related medically-attended visit will be defined as follows: hospitalization, emergency room (ER) visit, urgent care visit, physician's office visit, or telemedicine visit, with the primary reason for the visit being COVID-19.

Only medically-attended visits related to COVID-19, as determined by the investigator, will be recorded in the eCRF. Details will include at minimum:

- Type of visit (hospitalization, ER, urgent care, physician's office visit, telemedicine)
- Date of visit
- Primary reason for COVID-19 related medically-attended visit
- Treatments given for COVID-19 (including, but not limited to, concomitant medications and supplemental oxygen)
- If hospitalization due to COVID-19 was required, include length of visit, whether ICU care was given, or whether mechanical ventilation was required

Any adverse events or concomitant therapies reported to the investigator should be recorded on the respective Adverse Events eCRF or Concomitant Medications eCRF.

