5.3.5.10 Hospitalization or Prolonged Hospitalization

Any adverse event that results in hospitalization (i.e., inpatient admission to a hospital) or prolonged hospitalization should be documented and reported as a serious adverse event (per the definition of serious adverse event in Section 5.2.2), except as outlined below.

An event that leads to hospitalization under the following circumstances should not be reported as an adverse event or a serious adverse event:

- Hospitalization for a preexisting condition, provided that all of the following criteria are met:
 - The hospitalization was planned prior to the study or was scheduled during the study when elective surgery became necessary because of the expected normal progression of the disease
 - The patient has not experienced an adverse event
- Hospitalization based on local COVID-19 isolation policies, such as those in Japan: patients in these countries may be hospitalized for the sole purpose of isolation and not for severe symptoms or inpatient treatment. If deterioration that is judged by the investigator to have unexpectedly worsened in severity or frequency or changed in nature at any time during isolation, it should be recorded as an adverse event.

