Key Secondary: Proportion of patients with ≥ 1 COVID-19 related medically attended visit	Patients with ≥ 1 COVID-19 related medically attended visit through to study end (including early termination visits)	Treatment-policy strategy approach will be taken. Patients are followed, assessed and analyzed irrespective of their completion of the planned course of the study treatment and irrespective of rescue and concomitant therapy (contd.)	Composite strategy where patient considered as having the event if they die (contd.)	Difference in proportion of patients between treatments (contd.)	The outcome measure up to point of study withdrawal will be used (contd.)
Secondary: Proportion of patients with any post treatment infection	Patients with any post treatment infection through to study end (including early termination visits)		Not an intercurrent event as it is the outcome measure		
Key Secondary: Frequency (Proportion) of COVID-19 related complications (including hospitalizations and deaths)	Patients with a medically confirmed COVID-19 related complication through to study end (including early termination visits)				
Key Secondary: Proportion of patients with all-cause mortality	Patients with all-cause mortality through to study end (including early termination visits)				

Table 2 Estimands (cont.)

Endpoint	Variable or Outcome Measurement	Intercurrent Events		Population-Level Summary for the Variable	Handling of Missing Data
		Treatment Withdrawal/Rescue/Concomitant Medications	Death		
Secondary (Virology): Change from baseline in amount of SARS-CoV-2 virus RNA	Amount of SARS-CoV-2 virus RNA, as measured by RT-qPCR at Day 3, Day 5, Day 7 and Day 14	Treatment-policy strategy approach will be taken. Patients are followed, assessed and analyzed irrespective of their completion of the planned course of the study treatment and irrespective of rescue and concomitant therapy.	While on treatment approach where the outcome measure up to point of intercurrent event will be used	Difference in mean change from baseline between treatments	The outcome measure up to point of study withdrawal will be used
Secondary (Virology): AUC in amount of SARS-CoV-2 virus RNA	Amount of SARS-CoV-2 virus RNA, as measured by RT-qPCR to Day 14			AUC for each treatment	

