2.2 MULTIPLICITY ADJUSTMENT

The primary and key secondary endpoints ([Figure 2](#)) will be evaluated in a hierarchical manner with multiplicity control via multistage gatekeeping under the truncated Holm multiple testing procedure ([Dmitrienko et al. 2008](#)). In Families 1 and 2 of key secondary endpoints, the same truncation parameter value of 0.7 will be applied; no truncation is applied in Family 3, since it is prioritized lowest in the hierarchy and imposes no gatekeeping restrictions on subsequent families. The truncation parameter and the relative effect sizes of the endpoints influence how power is balanced over the secondary endpoint families. Truncation parameter values close to 1 should generally be chosen when the effect sizes in high-priority endpoints are relatively large in order to maximize overall power. In other settings where the effect sizes might be smaller or mixed, a truncation parameter value closer to 0 could improve overall power. A parameter value strictly less than 1 in testing families that impose parallel gatekeeping (i.e., at least one endpoint is considered statistically significant after multiplicity adjustment in order to test the next family) is needed to achieve strong overall type I error control ([Dmitrienko et al. 2009](#)).

Under this multistage gatekeeping approach, multiplicity-adjusted p-values will reflect the gatekeeping restrictions depicted in [Figure 2](#). In particular, the adjusted p-values for all key secondary endpoints in Families 1, 2, and 3 will be no smaller than the p-value for the primary endpoint. Similarly, the smallest adjusted p-value in Family 2 (3) will be no smaller than the smallest adjusted p-value in Family 1 (2). Endpoints for which the multiplicity-adjusted p-value is greater than 0.025 will not be considered statistically significant. These endpoints and all endpoints not under multiplicity control will be considered to provide supportive information. By repeated application of Proposition 4.1 of [Dmitrienko et al. \(2008\)](#), this testing strategy ensures that the overall type I error is no greater than 2.5%.

Figure 2 Multiple Testing Procedure for Endpoints

Ordering of endpoints within a family will be based on the p-value results from the hypotheses tests of the endpoints

COVID-19=coronavirus disease 2019; RT-qPCR=reverse-transcriptase quantitative polymerase chain reaction; SARS-CoV-2=severe acute respiratory syndrome coronavirus-2.

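### Isolation-only admissions are kept out of SAE reporting, and so out of the hospitalization endpoint, but nothing keeps them out of the key secondary medically-attended-visit endpoint

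*SAP*

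**What the plan says.** Isolation stays are expected. Protocol 3.1 says that patients in some countries "may be hospitalized for the sole purpose of isolation and not for severe symptoms or inpatient treatment". Protocol 4.1.2 relaxes the exclusion for prior or current hospital admission: "If local policy requires COVID-19 isolation or internment in a hospital or similar facility, such as in Japan", the exclusion may not apply to patients who are otherwise eligible.

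Protocol 5.3.5.10 lists among the events not to be reported as AEs or SAEs: "Hospitalization based on local COVID-19 isolation policies, such as those in Japan: patients in these countries may be hospitalized for the sole purpose of isolation". Unexpected deterioration during isolation is still to be recorded as an AE.

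The visit endpoint is defined in SAP 5.4.1.1: "COVID-19-related medically attended visits are defined as hospitalization, emergency room (ER) visit, urgent care visit", or an office or telemedicine contact, where COVID-19 is the main reason. Protocol 4.5.6.3 gives the same definition and adds a filter: "Only medically-attended visits related to COVID-19, as determined by the investigator, will be recorded in the eCRF". Neither section mentions isolation.

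SAP Table 2 labels the endpoint "Key Secondary: Proportion of patients with ≥ 1 COVID-19 related medically attended visit", so it falls under the gatekeeping procedure of SAP 2.2: "Endpoints for which the multiplicity-adjusted p-value is greater than 0.025 will not be considered statistically significant". The hospitalization endpoint in SAP 5.4.2.4 is only supportive, and is defined through SAEs attributed to the disease under study with an admission date.

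**The concern.** The sponsor has already decided, for safety reporting, that an isolation-only stay is not a clinical outcome. That decision reaches the supportive hospitalization endpoint through its SAE-based definition. It does not reach the alpha-controlled visit endpoint, whose definition is independent of SAEs. The same admission can thus be a non-event for the lesser endpoint and an event for the more important one.

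Local policy triggers these admissions whichever arm the patient is in. Counting them adds events that treatment cannot prevent, pulls the difference and the odds ratio toward no effect, and reduces the chance of a significant result on a confirmatory endpoint. If sites decide differently, the endpoint also means different things in different places.

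**Working it through.** **Tracing one case.** A patient is randomized and then admitted solely to isolate.

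- AE/SAE reporting (Protocol 5.3.5.10): not reported.
- Hospitalization endpoint (SAP 5.4.2.4): needs an SAE, so not an event.
- Visit endpoint (Protocol 4.5.6.3, SAP 5.4.1.1): the visit type is listed and no exception applies. It is an event if the investigator judges the visit COVID-19 related with COVID-19 as its main reason. An investigator could decide either way, and no instruction is given.

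**The plan's own figure.** The only power calculation is for the primary endpoint (Protocol 6.1, SAP 3). With hazard ratio 1.25, two-sided 0.025, 90% power and 2:1 allocation, the Schoenfeld formula gives (2.2414 + 1.2816)² / [(2/3)(1/3)(ln 1.25)²] = 12.411 / 0.011065 = 1,122 events, as stated. This point does not affect that figure. The documents give no rate, effect or power for the visit endpoint.

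**Dilution formula.** Let p be an arm's true visit rate. Let s be the share of patients, in either arm and regardless of true visit status, with a post-randomization isolation admission that is counted. Then:

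- observed rate p′ = p + s(1 − p)
- observed difference = (1 − s)(p0 − p1)

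If p0 = p1, then p0′ = p1′, so there is no type I error inflation.

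**Illustration A.** All rates and shares are assumptions. The efficacy-evaluable set of 1,248 at 2:1 gives 416 placebo and 832 active patients. Assumed true rates are 20% and 14%. Expected z = difference / √[p0′(1−p0′)/416 + p1′(1−p1′)/832], unstratified.

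| s | p0′ | p1′ | Difference (points) | Odds ratio | Expected z |
|---|---|---|---|---|---|
| 0% | 0.200 | 0.140 | 6.0 | 0.65 | 2.61 |
| 5% | 0.240 | 0.183 | 5.7 | 0.71 | 2.29 |
| 10% | 0.280 | 0.226 | 5.4 | 0.75 | 2.05 |
| 15% | 0.320 | 0.269 | 5.1 | 0.78 | 1.85 |

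**Illustration B.** Assumed relative risk 0.5, same patient numbers, power for two proportions (pooled variance under the null) at two-sided 0.025.

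| Assumed placebo rate | s = 0 | 1% | 2% | 5% | 10% |
|---|---|---|---|---|---|
| 5% | 52.8% | 42.3% | 34.9% | 22.2% | 13.5% |
| 10% | 84.0% | 78.7% | 73.6% | 59.5% | 42.4% |
| 20% | 99.3% | 98.9% | 98.5% | 96.4% | 90.7% |

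Example, placebo rate 10% and s = 5%: p0′ = 0.05 + 0.95 × 0.10 = 0.145; p1′ = 0.05 + 0.95 × 0.05 = 0.0975; difference 0.0475; observed relative risk 0.0975/0.145 = 0.67.

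**Stratification.** SAP 5.1 uses a Cochran-Mantel-Haenszel test stratified by region and high-risk factor. If every isolation case falls in the rest-of-world region, and that region holds one third of patients (an assumption), its within-stratum share is 3s. Combining two region strata with Mantel-Haenszel weights, at a 10% placebo rate, gives power of 73.9% at s = 2%, 61.5% at 5% and 48.1% at 10%. The unstratified figures are 73.6%, 59.5% and 42.4%. Stratification recovers part of the loss.

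**The case against.** The strongest answer is the investigator filter. Protocol 3.1 describes these stays as serving isolation and not treatment, and the endpoint requires COVID-19 to be the main reason for a medically attended visit. The form already asks for the visit type, main reason and treatments given. A careful investigator may well leave isolation out. This stands to the extent that a reader cannot infer that every isolation admission meets the definition; the documents make counting possible and site-dependent. It does not close the gap, because an isolation admission also exists because of COVID-19, and no section says which view to take.

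Other stronger readings do not hold either:

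- That isolation begun before randomization is by rule a non-event. SAP Table 2 gives an end to the counting period, study end, but no start.
- That the endpoint would fail against a fixed critical value of 2.24. That is the most lenient threshold. Truncated Holm with parameter 0.7 can ask for more: in a family of two (an assumption, since Figure 2 was not available for this check) the levels are 0.025/2 = 0.0125 and then 0.025 × (0.7 + 0.3/2) = 0.02125. Illustration B, run at 0.025, is best read for the relative loss.
- That the complications endpoint needs its own carve-out. SAP 5.4.1.3 counts only hospitalizations the investigator reports as complications, and Protocol 5.3.5.10 keeps isolation stays out of AE reporting.
- That deterioration during isolation is lost to the trial. Unexpected worsening is recorded as an AE, and death counts as an event in this endpoint. What is missing is a rule making non-fatal escalation within an existing stay a visit event.

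**Conclusion.** The point holds as an unreconciled definition: isolation-only admissions are outside SAE reporting and the supportive hospitalization endpoint, while the key secondary visit endpoint leaves them to site judgement. Any that are counted dilute the risk difference by (1−s) and cost power. This rests on the admissions being independent of arm and occurring after randomization.

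The size cannot be determined. Japan is named only as an example, and neither visit rates nor the share of patients under isolation policies is given. With few such patients the effect is negligible; at a 20% placebo rate and relative risk 0.5, even s = 5% costs about 3 points of power (99.3% to 96.4%). With a lower visit rate the same share costs far more. There is no false-positive risk and no effect on the primary endpoint. This is a cheap and worthwhile improvement, not a threat to the trial's main conclusion.

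**What to change.** In Protocol 4.5.6.3 and SAP 5.4.1.1, state before unblinding that hospitalization solely for COVID-19 isolation under local policy, as described in Protocol 5.3.5.10, is not a medically attended visit. State also that a stay which begins as isolation counts as an event if it becomes treatment of COVID-19 illness after randomization. Add an isolation-only yes/no item to the existing visit eCRF so that all sites apply the rule alike. No event date is needed for this purpose, because the endpoint is a proportion.

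The cost is one short addition to each document, one eCRF item and a slightly lower event count. No visits are added and the primary analysis does not change. Settling it before unblinding avoids a post hoc choice about which admissions count on an alpha-controlled endpoint.

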5.4.1.2 Time to Alleviation of Symptoms Maintained for a Duration of 21.5 Hours

Time to alleviation of symptoms defined as the time from randomization to the point at which a score of 0 or 1 for all Items 1-12 of the COVID-19 Symptom Diary is met and maintained for at least 21.5 hours.

For new symptoms (i.e., symptoms that develop due COVID-19 which present prior to or post baseline) and pre-existing symptoms (i.e., symptoms that existed prior to developing COVID-19) regardless of whether judged to be worse at screening:

- Alleviation of COVID-19 symptoms (i.e., a score of 0 [none] or 1 [mild] on the COVID-19 Symptom Diary):
 - Severe to mild, or none
 - Moderate to mild, or none

- Mild to mild or none
- None to mild or none

The same statistical methods as for the primary endpoint will be used as described in Section 5.3.2.

5.4.1.3 Frequency (Proportion) of Medically Confirmed COVID-19-Related Complications

COVID-19-related complications are defined as deaths and hospitalizations that are reported as COVID-19-related complications by the investigator, and medically confirmed COVID-19-related complications of radiologically confirmed pneumonia, acute respiratory failure, sepsis, coagulopathy, pericarditis/myocarditis, cardiac failure etc. The process of medical confirmation of certain events is briefly described in Section 1.2.2. The statistical method is detailed in Section 5.1. A sensitivity analysis of this endpoint using COVID-19-related complications as reported by the investigator will also be produced.

5.4.1.4 Time to One-Category Improvement of Baseline Presenting Symptoms Maintained for 21.5 Hours

Time to one-category improvement of baseline presenting COVID-19 for Items 1-12 of the COVID-19 Symptom Diary maintained for a duration of 21.5 hours defined as time from randomization to when the symptoms have improved by at least one category from baseline on the Likert scale, where improvement is defined as:

- For pre-existing symptoms (i.e., symptoms that existed prior to developing COVID-19) judged by the patient to be worse at screening OR for new symptoms (i.e., symptoms that develop due COVID-19 which present prior to or post baseline):
 - Improvement of at least one grade on the Likert scale from baseline if the severity at baseline is graded moderate or severe:
 - Severe to moderate, mild, or none
 - Moderate to mild or none
 - Mild to mild or none
 - None to mild or none
- For pre-existing symptoms (i.e., symptoms that existed prior to developing COVID-19) judged by the patient NOT to be worse at screening:
 - Maintained (no worsening) baseline severity:
 - Severe to severe, moderate, mild, or none
 - Moderate to moderate, mild or none
 - Mild to mild or none
 - None to none

Where the baseline assessment for COVID-19 symptom severity is missing, the patient will be excluded from the analysis.

The same statistical methods as for the primary endpoint will be used as described in Section 5.3.2.

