6.4.2 Secondary Efficacy Endpoints

The secondary efficacy endpoints for this study are as follows:

- *Time to alleviation or improvement of COVID-19 symptoms (Items 1–12 of the COVID-19 Symptom Diary) maintained for a duration of 43 hours, defined as follows:*
 - *For new symptoms: time from randomization to the alleviation of COVID-19 symptoms (i.e., a score of 0 [none] or 1 [mild] on the COVID-19 Symptom Diary)*
 - *For preexisting symptoms: time from randomization to when a patient's symptoms have been maintained or improved (Note: Improved requires at least a single category improvement from baseline on the COVID-19 Symptom Diary Likert scale.)*
- Time to alleviation of COVID-19 symptoms defined as the time from randomization to the point at which the following criterion is met and maintained for at least 21.5 hours:
 - Score of 0 or 1 for Items 1–12 of the COVID-19 Symptom Diary
- *Time to alleviation of COVID-19 symptoms defined as the time from randomization to the point at which the following criterion is met and maintained for at least 43 hours:*
 - *Score of 0 or 1 for Items 1–12 of the COVID-19 Symptom Diary*
- Time to one-category improvement of baseline presenting COVID-19 symptoms (*Items 1–12 of the COVID-19 Symptom Diary*) maintained for a duration of 21.5 hours defined as time from randomization to when the symptoms have improved by at least one category from baseline on the *COVID-19 Symptom Diary Likert scale*
- Time to alleviation of individual symptoms, defined as the time from randomization to the point at which the following criterion is met and maintained (for each individual symptom) for at least 21.5 hours:
 - Score of 0 or 1 for Items 1–14 of the COVID-19 Symptom Diary
- Proportion of patients requiring hospitalization for COVID-19

- Proportion of patients with ≥ 1 COVID-19 related medically attended visit through to study end (defined as hospitalization, ER visit, urgent care visit, physician's office visit, or telemedicine visit, with the primary reason for the visit being COVID-19) (see Section 4.5.6.3 for assessments to be done at weekly visits)
- Duration of fever (time to return to afebrile state [temperature $\leq 37.5^{\circ}\text{C}$] and remaining so for at least 21.5 hours) (see Section 6.4.1)
- Frequency of COVID-19 related complications (e.g., death, hospitalization, radiologically confirmed pneumonia, acute respiratory failure, sepsis, coagulopathy, pericarditis/myocarditis, cardiac failure)

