Key Secondary: Time to one-category improvement of symptoms	Time from randomization to one-category improvement of baseline presenting COVID-19 symptoms maintained for a duration of 21.5 hours, right censored at day 29 if the patient doesn't meet criteria	Treatment-policy strategy approach will be taken. Patients are followed, assessed and analyzed irrespective of their completion of the planned course of the study treatment and irrespective of rescue and concomitant therapy (contd.)	Hypothetical approach where patient censored at Day 29 if intercurrent event prior to achieving the endpoint (contd.)	Hazard ratio (contd.)	Patient censored at Day 29 if study withdrawal is prior to achieving the endpoint (contd.)
Secondary: Time to alleviation of individual symptoms	Time from randomization to alleviation an individual COVID-19 symptoms maintained for a duration of 21.5 hours, right censored at day 29 if the patient doesn't meet criteria				
Secondary: Time to return to afebrile state [temperature \leq 37.5C]	Time from randomization to return to afebrile state [temperature \leq 37.5C] maintained for a duration of 21.5 hours for a patient with fever at baseline, right censored at day 29 if the patient doesn't meet criteria				
Secondary: Proportion of patients requiring hospitalization for COVID-19	Patients requiring hospitalization for COVID-19 through to study end (including early termination visits)		Composite strategy where patient considered as having the event if they die	Difference in proportion of patients between treatments	The outcome measure up to point of study withdrawal will be used

Table 2 Estimands (cont.)

Endpoint	Variable or Outcome measurement	Intercurrent Events		Population-Level Summary for the Variable	Handling of Missing Data Study Withdrawal/ Lost to Follow-Up
		Treatment Withdrawal/ Rescue/ Concomitant Medications	Death		

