Time to alleviation of individual symptoms (Items 1-14 of the COVID-19 Symptom Diary) is defined separately for each symptom as the time from randomization to the point at which a score of 0 or 1 for the individual symptom is met and maintained for at least 21.5 hours in patients with a symptom score ≥ 2 at baseline. The endpoints corresponding to each of the symptoms are as follows:

- Time to alleviation of nasal congestion or runny nose
- Time to alleviation of sore throat
- Time to alleviation of cough
- Time to alleviation of shortness of breath
- Time to alleviation of muscle or body aches
- Time to alleviation of fatigue
- Time to alleviation of headache
- Time to alleviation of chills/sweats
- Time to alleviation of feeling hot or feverish

- Time to alleviation of nausea
- Time to alleviation of vomiting
- Time to alleviation of diarrhea
- Time to alleviation of sense of smell
- Time to alleviation of sense of taste

The same statistical methods as for the primary endpoint will be used as described in Section [5.3.2](#).

Where a baseline assessment for COVID-19 symptom severity is missing for an individual symptom, the patient will be excluded from the analysis.

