5.7.2.2 Baseline Disease Characteristics

- SARS-CoV-2 RT-PCR Status at Baseline
- Baseline viral load
- Seropositive status at baseline
- Presence of a high-risk factor
- Presence of individual high-risk factors
- Time from symptom onset to study treatment in days
- Number of symptoms present at baseline
- Number of symptoms from pre-existing conditions at baseline
- Number of symptoms with score ≥ 2 present at baseline
- Vaccinated for COVID-19
- Baseline systemic corticosteroid use
- Baseline inhaled corticosteroid use

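### SAP 5.4.1.4 names its key secondary endpoint for symptoms present at baseline, but its scoring rows also count symptoms that appear later, and the qualifying baseline score is never defined

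*SAP*

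**What the plan says.** Three places limit the endpoint to symptoms the patient presented with:

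- Protocol 6.4.2 lists "Time to one-category improvement of baseline presenting COVID-19 symptoms".
- SAP Table 2 (section 1.1) gives the estimand variable as "Time from randomization to one-category improvement of baseline presenting COVID-19 symptoms maintained for a duration of 21.5 hours".
- The lead sentence of SAP 5.4.1.4 begins "Time to one-category improvement of baseline presenting COVID-19 for Items 1-12 of the COVID-19 Symptom Diary", and its heading uses the same restriction.

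The lead sentence then says the event occurs "when the symptoms have improved by at least one category from baseline on the Likert scale, where improvement is defined as" and passes to a list of scoring rows. The first block of rows covers pre-existing symptoms that the patient judged worse at screening. It also applies "for new symptoms (i.e., symptoms that develop due COVID-19 which present prior to or post baseline". An item in this block rated None at baseline must be mild or none. The second block covers pre-existing symptoms judged not worse; there an item rated None must stay at none.

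Table 2 labels the endpoint a key secondary, and SAP 2.2 places key secondaries under multiplicity control. SAP Appendix 1, which lists changes from the protocol's planned analyses, does not mention this endpoint.

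**The concern.** A symptom that first appears after baseline is not a baseline presenting symptom, and an item rated None at baseline has nothing to improve. The title and estimand point to one set of items and the rows to a larger one. The same diary can therefore give two event times, depending on which text the programmer follows.

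This endpoint belongs to the confirmatory testing strategy, so one derivation should be fixed before treatment codes are opened. SAP 5.3.3 does restrict to baseline presenting symptoms in a sensitivity analysis, but only for the primary endpoint. Nothing planned would show how much the choice matters here.

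**Working it through.** The plan gives no figure for this endpoint to reproduce. The sample size in SAP section 3 rests on the primary endpoint and plays no part. The check compares the texts and then applies the readings to scores.

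**1. Is the term a real restriction?** Yes. SAP 5.3.3 contrasts a sensitivity analysis that requires only baseline presenting symptoms to qualify with the 12-item rule of the primary endpoint. The phrase therefore narrows the item set elsewhere in the same SAP.

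**2. Does it have a threshold?** No. SAP 5.4.2.2 restricts the individual-symptom endpoints by score, "in patients with a symptom score ≥ 2 at baseline", but 5.4.1.4 does not refer to that rule. SAP 5.7.2.2 tabulates "Number of symptoms present at baseline" separately from "Number of symptoms with score ≥ 2 present at baseline". This suggests that being present means at least mild, but does not define it.

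**3. Where do the readings differ?** Scores run from 0 (none) to 3 (severe). *Rows* means all 12 items scored as printed. The other two columns score only items at or above the baseline cut-off.

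| Symptom type | Baseline | Later score | Rows | Cut-off 1 or more | Cut-off 2 or more |
|---|---|---|---|---|---|
| New, or pre-existing and worse | None | Moderate or severe | Fails | Not scored | Not scored |
| Pre-existing, not worse | None | Mild, moderate or severe | Fails | Not scored | Not scored |
| Any type | Mild | Moderate or severe | Fails | Fails | Not scored |

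For items rated moderate or severe at baseline, all three readings apply the same rows and agree.

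**4. How many items are scored?** Twelve under the rows. Protocol 4.1.1 requires at least three of the same 12 symptoms at score 2 or more. If the baseline diary still matches that screening criterion, a cut-off of 2 or more scores between 3 and 12 items.

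**5. Hypothetical diary.** Assume entries at 07:00 and 22:00. Three new presenting items fall from moderate to mild on Day 6 morning and stay there. Nausea is a new symptom, None at baseline, and moderate from Day 5 through Day 9 bedtime, then none. All other items stay at none. SAP 5.1 requires every non-missing assessment to qualify until at least 21.5 hours have been shown.

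- *Presenting items only:* the criterion is first met on Day 6 at 07:00. At 22:00 that day, 22 − 7 = 15 hours have passed, which is too short. At 07:00 on Day 7, 24 hours have passed, and 24 ≥ 21.5. The event is on Day 6.
- *Rows as printed:* nausea fails through Day 9. All items first qualify on Day 10 at 07:00, confirmed 24 hours later on Day 11. The event is on Day 10.
- *Difference:* 10 − 6 = 4 days. If the nausea persisted to Day 29, the rows would give a patient censored at Day 29 instead of an event on Day 6.

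**6. The row that holds an item at none.** Change the diary so that nausea is pre-existing, not worse, None at baseline, and only mild on Days 5 to 9. The rows of 5.4.1.4 still give Day 10. The primary endpoint in 5.3.1, and its 43-hour version in 5.4.2.1, accept mild for such an item, so the primary event falls on Day 6. On this row the one-category endpoint is harder to meet than the primary, and no reason is given.

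**The case against.** The strongest reply is that the rows are explicit and use the same format as 5.3.1, 5.4.1.2 and 5.4.2.1. They can be programmed as they stand, whereas the restricted reading cannot, because it has no cut-off. On that view the rule is fully specified and only the label is wrong. This is fair as far as it goes, and the documents do not settle which was intended. It does not remove the problem: following the rows produces an endpoint other than the one in the title, the protocol and the estimand table, and the departure is undeclared. The wording may have been carried over from the primary endpoint, where all 12 items do count, but that is inference.

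A reader might also infer that 5.4.1.4 contradicts itself by asking for a one-category improvement while passing mild items that stay mild and pre-existing items that are merely maintained. The documents do not support this. The lead sentence hands the definition of improvement to the rows. The one-grade requirement applies only to items graded moderate or severe at baseline, and the maintenance rule for symptoms judged not worse is written out. Protocol section 6 leaves detailed specifications to the SAP, so these rows are operational detail and need no entry in Appendix 1.

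The consequence is also limited: the endpoint is tested only behind the primary. Its place in the hierarchy cannot be seen, because the figure that shows it is not reproduced.

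**Conclusion.** The mismatch is real and confined to scope. The rows of SAP 5.4.1.4 score symptoms outside the endpoint's stated estimand, and the term that should limit them has no score. Under the rows as printed, a symptom absent at baseline can delay or block the event after every presenting symptom has improved.

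The four-day gap shows that event times can move; it rests on an invented diary and does not estimate a typical effect. The share of patients affected depends on how often absent items become moderate or severe (or mild, for the pre-existing, not-worse group) around the time the presenting items qualify. The documents give no such rates. A reader might infer a threat to the primary result or to type I error control; nothing here supports that, since neither the primary definition nor the testing procedure is touched. The issue should be settled before unblinding because it concerns a key secondary endpoint under multiplicity control.

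**What to change.** Before unblinding, make the rule match the estimand in 5.4.1.4:

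1. Define baseline presenting by an explicit baseline diary score. At least mild would fit the tabulation in 5.7.2.2, but that is an assumption; 5.4.2.2 uses 2 or more.
2. Score only those of Items 1–12 that meet it.
3. Delete the words that bring in symptoms appearing after baseline, and both None rows. With a cut-off of 2 or more, the mild rows also lose their function and should go.
4. State how a patient with no qualifying item at baseline is handled, for example excluded, as 5.4.2.2 does for patients below its threshold.

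If all 12 items are meant to count, keep the rows but rename the endpoint, amend Table 2, list the change in Appendix 1, and align the row that holds a pre-existing, not-worse item at none with 5.3.1, which accepts mild.

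Either route costs SAP wording and derivation code only. No new data are needed.
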